5.5.7. Household Contacts

The number and percentage of participants with any documented asymptomatic SARS-CoV-2 or symptomatic COVID-19 infection in one or more household contacts as of Day 29 will be summarized by treatment group in the mFAS-non-Omicron analysis set. Among those participants with household contacts with asymptomatic and symptomatic infection, descriptive summary statistics for the number of household contacts with each type of infection will be summarized using percentages based on the number of participants with household contacts with documented asymptomatic or symptomatic COVID-19 infection.

These data will also be presented in a listing.

5.5.8. COVID-19-Related Mortality Through Day 29

The number and percentage of participants with a COVID-19 related death, with COVID-19 as the primary cause of death, and with COVID-19 or COVID-19 complications contributory to death will be summarized in the mFAS-non-Omicron by treatment group.

The listing of deaths will include a column for primary cause of death and if COVID-19 or COVID-19 complications were contributory to death.

5.5.9. Post-Acute Sequelae of SARS-CoV-2 Infection

During the long-term follow-up period, participants will be asked questions about their overall health status including return to usual health and usual activities and any ongoing symptoms associated with COVID-19 at the visits specified in the Schedule of Events ([Appendix M](#)). Symptoms reported on the Long-term Health Status Assessment eCRF will be considered PASC events. The number and percentage of participants with any PASC will be summarized by treatment group and in those participants with and without a COVID-19-related hospitalization through Day 29 with respect to the mFAS-non-Omicron. The number and percentage of participants reporting each symptom thought to be related to COVID-19 and the number and percentage of participants returning and not returning to usual health and usual activities will be summarized by treatment arm. The number of participants in each arm reporting no symptoms, 1 ongoing symptom and >1 ongoing symptom will be summarized at Day 60, Day 90, and Month 6. The overall severity of PASC symptoms will be presented (absent, mild, moderate, severe) by treatment arm and time point (Day 60, Day 90, and Month 6).

These data will also be presented in a listing.

5.6. Subgroup Analyses

The primary (Estimand 1a) and key secondary (Estimands 2 and 3) analyses will be repeated within the subgroups listed below in the mFAS-non-Omicron analysis set. Analyses of virologic endpoints will be repeated within selected subgroups as detailed below.

- age group (12-17, 18-65, >65, ≥ 50 , >55, and >75 years)
- sex (male, female)
- race (White, Black or African American, Asian, American Indian or Alaska Native, Native Hawaiian or Other Pacific Islander, Other, Multiple)
- time from symptom onset to the date of study drug administration (0-3, 4-5, >5 days)
- time from SARS-CoV-2 test to the date of study drug administration (0, 1-2, 3-5, >5 days)
- baseline SARS-CoV-2 status by RT-qPCR from NP swab (positive, negative).
- baseline viral load from NP swab (>5 , ≤ 5 \log_{10} copies/mL); viral load >5 and >4 \log_{10} copies/mL on Day 7 based on the NP sample will also be analyzed in these subgroups
- baseline qualitative serologic status (positive, negative) from the assay of antibodies to SARS-CoV-2 N antigen.
- baseline overall serologic status (positive, negative) from three assays: antibodies to N antigen, IgA to S (spike) trimer, IgG to S trimer; viral load >5 and >4 \log_{10} copies/mL on Day 7 based on the NP sample will also be analyzed in these subgroups
- COVID-19 severity (mild, moderate)

- BMI (≥ 30 and $\geq 40 \text{ kg/m}^2$ for adults and $\geq 85^{\text{th}}$ percentile by age and sex based on CDC growth charts for adolescents, $<30 \text{ kg/m}^2$ for adults and $<85^{\text{th}}$ percentile by age and sex based on CDC growth charts for adolescents) ([CDC 2001](#))
- Diabetes as collected on COVID-19 Risk Factors eCRF (yes, no)
- Cardiac disease as collected on COVID-19 Risk Factors eCRF (yes, no)
- WGS confirmed non-Omicron variant (Delta/Delta-like, etc)

Given the various sample sizes by subgroup, the standardized relative risk reduction will be estimated using the same methodology in [Ge et al. \(2011\)](#) from a logistic regression model fit to the binary endpoint with age (continuous) as covariate for each subgroup with at least 5 total events. Subgroups with less than 5 total events will be summarized descriptively.

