4.2. Sample Size

The primary analysis is the comparison of the ADG20 arm versus the placebo arm with respect to proportion of participants infected with a non-Omicron variant of SARS-CoV-2 with a COVID-19-related hospitalization or all-cause death through Day 29.

The original required sample size was calculated based on the following assumptions obtained from a review of data from studies of other mAbs in participants with a high risk for disease progression leading to hospitalization or death prior to widespread emergence of both the Delta and Omicron variants ([AstraZeneca 2022](#); [Eli Lilly and Company 2022](#); [GlaxoSmithKline 2021](#); [Regeneron 2022](#)). The original sample size of 1084 participants was planned with 90% power, 2-sided alpha .05, and a 1:1 randomization ratio to detect a statistically significant risk reduction with a true efficacy of relative risk reduction 70% and a 5% event rate in the placebo arm.

At the time of enrollment suspension in January 2022, a total of 399 participants were randomized. Of them, approximately 320 participants will be included in the primary efficacy population of participants with a non-Omicron variant of SARS-CoV-2. Based on blinded monitoring of the primary endpoint outcomes, an aggregate event rate of approximately 9% was observed, indicating a higher placebo event rate than previously assumed and providing approximately 80% power to test the primary endpoint in the primary efficacy population given an estimated placebo event rate of 12% and the same efficacy assumption.

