5.5.6. Graphical Displays of Efficacy Endpoints

Forest plots for the standardized relative risk reduction for the primary and two binary key secondary endpoints will be provided. Additionally, adjusted, and unadjusted mean change from baseline in viral load will be depicted with forest plots, box and whisker plots and line plots.

Duration of viral shedding, time to sustained recovery of symptoms, time to symptom improvement, and time to symptom resolution will be presented using Kaplan-Meier plots and forest plots. Finally, a Kaplan-Meier plot for all-cause death will be provided.

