APPENDIX J. ALGORITHM OF LOGISTIC REGRESSION METHOD

The method described in [Ge et al. \(2011\)](#) computes a population-level estimate for the treatment difference (in terms of risk difference in proportions) and supports an adjustment for the pre-defined prognostic factors.

With a data set of n participants, binary response vector $Y = (y_1, y_2, \dots, y_n)'$, covariate matrix $X = (x_1, x_2, \dots, x_n)'$, a logistic regression model assumes $\text{logit}[P(y_i = 1 | x_i)] = \beta'x_i$, where $\text{logit}(p) = \ln[p/(l - p)]$.

Let b denote the maximum likelihood estimate (MLE) of β , and its estimated variance-covariance matrix is V .

The proportions of responders to both treatment and control, and their risk difference are estimated as follows.

First, create the new covariate matrix X_t from X by adjusting the column corresponding to treatment assignment such that all participants are in the treated group. Then calculate the vector of estimated probabilities of response to treatment \hat{P}_t from X_t and b , $\hat{P}_t = \text{logit}^{-1}(X_t b)$. Similarly, assume each participant is assigned to control and redo the above steps to get X_c and \hat{P}_c .

Risk difference (RD) in proportions:

$$RD = \sum_{i=1}^n \frac{\hat{P}_{ti}}{n} - \sum_{i=1}^n \frac{\hat{P}_{ci}}{n}$$

where \hat{P}_{ti} and \hat{P}_{ci} are the i^{th} elements of \hat{P}_t and \hat{P}_c respectively.

The variance of the estimated risk difference:

$$\text{Var}(RD) = \text{Var}\left(\sum_{i=1}^n \frac{\hat{P}_{ti}}{n}\right) - 2\text{cov}\left(\sum_{i=1}^n \frac{\hat{P}_{ti}}{n}, \sum_{i=1}^n \frac{\hat{P}_{ci}}{n}\right) + \text{Var}\left(\sum_{i=1}^n \frac{\hat{P}_{ci}}{n}\right)$$

The delta method can be used to estimate each component of the variance estimation.

Define A_t as a vector with elements $A_{ti} = \hat{P}_{ti}(1 - \hat{P}_{ti})$. Similarly define A_c as a vector with elements $A_{ci} = \hat{P}_{ci}(1 - \hat{P}_{ci})$.

$$d_t = (A_t'X_t)/n$$

$$d_c = (A_c'X_c)/n$$

$$SE = \sqrt{(d_t V d_t' + d_c V d_c' - 2 d_c V d_t')}$$

The confidence interval of RD is $RD \pm Z_{(1-\alpha/2)} SE$

Log risk ratio (RR) in proportions:

$$\delta_1 = \log(RR) = \log \sum_{i=1}^n \frac{\hat{P}_{ti}}{n} - \log \sum_{i=1}^n \frac{\hat{P}_{ci}}{n}$$

where \hat{P}_{ti} and \hat{P}_{ci} are the i^{th} elements of \hat{P}_t and \hat{P}_c respectively.

The variance of the estimated log risk ratio:

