$$Var(\delta_1) = Var(\log \sum_{i=1}^n \frac{\hat{P}_{ti}}{n}) - 2cov\left(\log \sum_{i=1}^n \frac{\hat{P}_{ti}}{n}, \log \sum_{i=1}^n \frac{\hat{P}_{ci}}{n}\right) + Var(\log \sum_{i=1}^n \frac{\hat{P}_{ci}}{n})$$

Consider,

$$\begin{aligned} Var\left(\log \sum_{i=1}^n \frac{\hat{P}_{ti}}{n}\right) &\approx \left(\frac{1}{\sum_{i=1}^n \frac{\hat{P}_{ti}}{n}}\right)^2 Var\left(\sum_{i=1}^n \frac{\hat{P}_{ti}}{n}\right) \approx \left(\frac{1}{\sum_{i=1}^n \frac{\hat{P}_{ti}}{n}}\right)^2 d_t V d_t' \\ Var\left(\log \sum_{i=1}^n \frac{\hat{P}_{ci}}{n}\right) &\approx \left(\frac{1}{\sum_{i=1}^n \frac{\hat{P}_{ci}}{n}}\right)^2 Var\left(\sum_{i=1}^n \frac{\hat{P}_{ci}}{n}\right) \approx \left(\frac{1}{\sum_{i=1}^n \frac{\hat{P}_{ci}}{n}}\right)^2 d_c V d_c' \\ 2cov\left(\log \sum_{i=1}^n \frac{\hat{P}_{ti}}{n}, \log \sum_{i=1}^n \frac{\hat{P}_{ci}}{n}\right) &\approx 2 \left(\frac{1}{\sum_{i=1}^n \frac{\hat{P}_{ti}}{n}}\right) \left(\frac{1}{\sum_{i=1}^n \frac{\hat{P}_{ci}}{n}}\right) d_c V d_t' \end{aligned}$$

$$SE(\delta_1) = \sqrt{Var(\delta_1)}$$

The confidence interval of $\log(RR)$ is $\delta_1 \pm Z_{(1-\alpha/2)} SE(\delta_1)$. The confidence interval of RR is $\exp(\delta_1 \pm Z_{(1-\alpha/2)} SE(\delta_1))$.

The relative risk reduction and its confidence interval is $(1 - \exp(\delta_1))$ and $[1 - \exp(\delta_1 + Z_{(1-\alpha/2)} SE(\delta_1)), 1 - \exp(\delta_1 - Z_{(1-\alpha/2)} SE(\delta_1))]$.

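### The SAP 5.6 threshold of 5 events pooled over arms sends subgroups with no events in one arm to a logistic model that has no maximum likelihood estimate, so the RRR interval is unusable

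*SAP*

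**What the plan says.** SAP 5.6 repeats the primary analysis and the first two key secondary analyses (Estimands 1a, 2 and 3) within a long list of subgroups of the mFAS-non-Omicron set. For the binary endpoints, "the standardized relative risk reduction will be estimated using the same methodology in" the 2011 covariate-adjustment paper, from a logistic model "with age (continuous) as covariate for each subgroup with at least 5 total events". The only fallback is this: "Subgroups with less than 5 total events will be summarized descriptively". The count pools the two arms, and no minimum is set within an arm.

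Appendix J gives the algorithm. It lets b "denote the maximum likelihood estimate (MLE) of" the logistic coefficients, with no penalty term. It standardizes the predicted risks under each treatment and forms a Wald interval on the log risk ratio. "The relative risk reduction and its confidence interval is" then obtained by back-transforming.

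SAP 5.5.6 adds: "Forest plots for the standardized relative risk reduction for the primary and two binary key secondary endpoints will be provided". That sentence does not say whether the plots are by subgroup.

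Neither document says what to do when an arm has no events. There is no penalized or exact logistic regression, no continuity correction and no score-interval fallback.

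**The concern.** The authors clearly foresaw sparse subgroups, since 5.6 explains the reduced covariate set by the varying subgroup sizes. But the threshold counts the wrong quantity. Whether the treatment coefficient can be estimated depends on having events in both arms, not on the pooled total. A split of 5 placebo events to 0 on ADG20 passes the rule and must be modelled, yet the model then has no maximum likelihood solution for treatment.

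An effective drug makes this split more likely. The printed interval would then depend on the software's stopping rule. SAP 3.2 requires analysis decisions to be made blinded and the SAP to be signed before unblinding. Without a rule, the repair would be chosen once it was known which subgroups had no ADG20 events.

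**Working it through.** **Inputs.** From SAP 4.2: about 320 participants in the primary efficacy population (about 160 per arm), 1:1 allocation, an estimated placebo rate of 12%, and the original design's "true efficacy of relative risk reduction 70% and a 5% event rate in the placebo arm". The 70% reduction is retained, so the ADG20 rate is 0.12 × 0.30 = 3.6%. Subgroup sizes and ages are not in the documents and are assumptions below.

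**The plan's own figure.** The 5-event threshold has no derivation to reproduce, but the power from the same rates does. The pooled rate is (0.12 + 0.036)/2 = 0.078. With 160 per arm:

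z = [0.084·√160 − 1.96·√(2·0.078·0.922)] / √(0.12·0.88 + 0.036·0.964) = (1.0625 − 0.7433)/0.3746 = 0.852

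This gives 80.3% power, which agrees with the stated 80% or so. The rates are not in dispute.

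**Step 1: what Appendix J returns with an empty ADG20 arm.** The likelihood keeps rising as the treatment coefficient goes to minus infinity. In the variance of log RR, the ADG20 term is d_t V d_t′ divided by the squared mean ADG20 risk. Both d_t and that risk shrink to 0 at the same rate, so SE(log RR) follows the SE of the treatment coefficient, which grows without limit. Appendix J was coded with treatment and age and run on 5/40 placebo v 0/40 ADG20, with illustrative ages:

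| Newton-Raphson iterations | Treatment coefficient | RRR | SE(log RR) | RRR lower limit |
|---|---|---|---|---|
| 8 | −7.3 | 99.9% | 15.7 | about −1.8 × 10¹²% |
| 15 | −14.3 | 100% | 520 | minus infinity |
| 25 | −24.3 | 100% | about 77,000 | minus infinity |

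The upper limit is 100% throughout. A case of 7/60 v 0/60 behaves the same way. The divergence does not depend on the ages or the subgroup size. With all events on ADG20 instead, the RRR diverges to minus infinity, but that split is far less likely if the drug works.

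**Step 2: how often the rule is met with no ADG20 event.** With m per arm:

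P = (1 − 0.036)^m × P[Binomial(m, 0.12) ≥ 5]

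For m = 40 this is 0.2307 × 0.5331 = 12.3%. The last column divides P by the chance that the subgroup reaches 5 events at all.

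| Per arm (assumed) | P(at least 5 events, none on ADG20) | Share of qualifying subgroups |
|---|---|---|
| 20 | 4.0% | 20% |
| 30 | 9.6% | 19% |
| 40 | 12.3% | 16% |
| 50 | 11.7% | 13% |
| 60 | 9.5% | 10% |
| 80 | 5.2% | 5% |
| 100 | 2.5% | 2.5% |
| 140 | 0.6% | 0.6% |
| 160 (whole set) | 0.3% | 0.3% |

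As a cross-check, given k events in total, the chance that all are on placebo is about (1/1.3)^k: 27% at k = 5, 16% at 7 and 7% at 10.

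**Step 3: does a per-arm minimum cure it?** With 5/40 v 1/40 the same code gives RRR 80% with 95% CI −64% to 98%, which is wide but finite. For 5/40 v 0/40 the Miettinen-Nurminen interval for the observed risk difference (placebo minus ADG20) is 3.1 to 26.2 percentage points, so an informative interval remains available.

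**The case against.** The strongest reply is that the failure announces itself and that nothing confirmatory rests on it. Much of this stands.

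- **False precision.** A reader might infer that the plan would publish a convincing 100% subgroup effect. The documents do not support that. When one arm is empty, 100% is the observed RRR, and the Appendix J interval becomes unbounded, not narrow.
- **Risk difference.** One might suppose that its interval fails too. The standardized risk difference stays finite: for 5/40 v 0/40 it is −12.7 points (ADG20 minus placebo), Wald interval −23.0 to −2.3. The modelled measure named in 5.6 is the RRR.
- **Multiplying up.** It is tempting to multiply 10–12% by the many subgroup levels and three endpoints. The levels overlap (several nested age cuts, two serostatus definitions), so the failures are correlated, and sparse levels fall to the descriptive rule. An even two-way split gives about 80 per arm, where the figure is 5%. Both binary key secondary endpoints include the primary events (SAP 3.5.1), so they have at least as many events and the 12% v 3.6% rates do not apply.
- **Confirmatory tests.** Subgroup results lie outside the testing hierarchy, and the whole primary set has a 0.3% chance of an empty ADG20 arm.
- **Ordinary practice.** A programmer would probably print a not-estimable footnote. The SAP does not say so, however, and its fallback excludes these subgroups.

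What remains is that the written rule requires a model with no solution in cases that the plan's own rates make plausible.

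**Conclusion.** The rule is wrong as written; the severity is minor. In any subgroup that reaches 5 events with none in one arm, SAP 5.6 calls for an RRR interval that the Appendix J method cannot supply. This part is mathematical and needs no assumption.

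The frequency does rest on assumptions: the SAP's primary-endpoint rates of 12% and 3.6%, equal arms within the subgroup, and a subgroup size that the documents do not state. It peaks at about 12% near 40 per arm and falls to 5% at 80 and under 1% at 140. It applies to one subgroup at a time and to the primary endpoint only. The reach is limited to the supportive subgroup results and any forest plots of them. The primary and key secondary tests are not called into question.

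**What to change.** Change the SAP 5.6 criterion to *at least 5 total events and at least 1 event in each arm*. For every other subgroup, show counts by arm with the Miettinen-Nurminen interval for the observed risk difference, as already specified in SAP 5.5.1, and mark the RRR interval not estimable. This also covers subgroups with no placebo events.

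The cost is a sentence or two in the SAP, settled before unblinding. A few subgroups lose a model-based RRR, but its interval would not have been valid. Subgroups with a single ADG20 event will still have very wide intervals. Penalized or exact logistic regression, or a score interval for the risk ratio, would be a workable alternative if a ratio measure is wanted in every row; the choice only needs to be fixed in advance.

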5.7. Other Analyses

5.7.1. Resistance

Resistance to ADG20 in viral isolates obtained from participants will be characterized using genotypic methods, with phenotypic methods deployed as appropriate. Plans for analysis of resistance data will be provided in the Resistance Monitoring Plan. A summary of participants with baseline and post-baseline (treatment-emergent) variations at critical amino acid positions associated with ADG20 resistance ($\geq 15\%$ and $\geq 50\%$ allele frequencies) and their associated virologic and clinical outcomes will be provided in the FAS.

5.7.2. Immunogenicity Analyses

Analyses will be conducted in the Immunogenicity Set. ADA status will be defined as positive or negative based on the confirmatory cut-off point. ADA results will be summarized by treatment arm at baseline (predose Day 1), Days 29 and 90, and Months 6 and 11. ADA status (positive or negative) is determined based on the confirmatory assay results.

Treatment-emergent ADA is defined as participants who had a negative ADA measurement at baseline (predose Day 1) and positive ADA post-baseline (Day 29, Day 90, Month 6, or Month 11) or participants who had a positive ADA measurement at baseline and a positive ADA measurement post-baseline with an ADA titer ≥ 4 times the baseline ADA titer. The number and percentage of patients with treatment-emergent ADA will be summarized by treatment arm. The frequency of neutralizing antibodies (if assessed) may also be summarized.

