6.7. Immunogenicity

Blood samples to provide serum for detection of ADA (and neutralizing antibody) against ADG20 will be collected at timepoints specified in the Schedule of Assessments ([Table 12-1](#)). In addition to samples collected at scheduled visits, an additional blood sample should be collected from participants experiencing hypersensitivity reactions as described in Section [6.8.2](#). Additional instructions for sample collection, processing, storage, and shipping will be provided in the laboratory manual.

Immunogenicity may be assessed by a validated assay designed to detect ADAs in the presence of ADG20 at a laboratory approved by the sponsor or designee. Antibodies may be further characterized for their ability to neutralize the activity of ADG20. The sample analysis will follow a tiered approach of screening, confirmation, and titer determination.

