7.12. Immunogenicity

Immunogenicity data will be listed, and summarized in tables using descriptive statistics, including rates, titers, and neutralization data, as appropriate. Associations between immunogenicity data and PK as well as safety and efficacy data will be explored. Details of immunogenicity analysis will be provided in the SAP.

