Visit windowing rules: Assessments collected on the nominal visits per the protocol schedule will be included in by-visit summaries and analysis. If an assessment is missing from a nominal visit, available assessments from the unscheduled visits within the protocol-defined target-study-day range may be mapped to the corresponding nominal visit. The assessment occurring closest to the target study day will be used. If there are multiple assessments equally distant to the target study day, the earliest assessment will be used.

All diary data will be summarized based on the actual day.

Incomplete/missing data:

Imputation rules for missing dates of prior/concomitant medications, including COVID-19 vaccinations and prohibited medications, and procedures are provided in [Appendix C](#).

Imputation rules for missing AE are provided in [Appendix D](#).

Data that are continuous in nature but are reported in the form $< x$, $> x$, $\leq x$, or $\geq x$ (where x is considered as the limit of quantitation) will be set to limit of quantitation value with the following exceptions:

- For viral load data:
 - Viral load values reported as detected but BLQ of the PCR assay (<714 copies/mL) are imputed with half of LLOQ of the PCR assay (ie, 357 copies/mL)
 - Viral load values reported as not detected are imputed with 1 copy/mL (ie, $0 \log_{10}$ copies/mL)
 - All viral load analyses will use both observed and imputed viral load data. Listings present both observed and imputed viral load.
- For PK concentrations
 - Serum concentrations that are BLQ will be treated as zero for PK analyses, except for BLQ values observed between 2 quantifiable concentrations, which will be set to missing. If consecutive BLQ concentrations are followed by quantifiable concentrations in the terminal phase, those concentrations after BLQ concentrations will be treated as missing. Missing concentrations will be treated as missing in the PK parameter calculations.
- Efficacy endpoint data will be imputed as detailed in Section [5.5](#).
- Other incomplete/missing data will not be imputed, unless specified otherwise.

Treatment groups: The following treatment groups will be used for summary purposes:
ADG20, Placebo

All analyses and data summaries/displays for efficacy will be provided by treatment group using the appropriate analysis population unless otherwise specified.

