4.5.7. Immunogenicity Set

The Immunogenicity Set includes all participants who received any study drug, had a valid immunogenicity test result before the dose of study drug, and had at least 1 valid result after the dose of study drug.

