7. CHANGES IN THE PLANNED ANALYSIS

There are no changes to the analyses presented in the protocol.

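### One limb of the treatment-emergent ADA definition leaves out the hypersensitivity reaction sample, and the SAP plans ADA associations with PK only

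*SAP*

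**What the plan says.** **The sample.** Protocol 6.7 states that, beyond the scheduled draws, "an additional blood sample should be collected from participants experiencing hypersensitivity reactions as described in Section" 6.8.2. Section 6.8.2 asks for PK and ADA samples at an unscheduled visit when a reaction is reported after Day 4 and away from a scheduled in-person visit. Section 6.4.1.1 refers to the same visit without repeating the Day 4 limit. ADA incidence is a secondary endpoint in both documents.

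**The definition.** SAP 5.7.2 has two limbs. The baseline-negative limb requires "positive ADA post-baseline (Day 29, Day 90, Month 6, or Month 11"). The baseline-positive limb covers "participants who had a positive ADA measurement at baseline and a positive ADA measurement post-baseline with an ADA titer" at least four times the baseline titer, and lists no visits. The by-visit summary follows the schedule: "ADA results will be summarized by treatment arm at baseline (predose Day 1), Days 29 and 90, and Months 6 and 11".

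**The denominator.** The Immunogenicity Set (SAP 4.5.7) takes dosed participants with a valid pre-dose result who "had at least 1 valid result after the dose of study drug". SAP 4.1 makes the analysis set the default denominator for percentages.

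**Unscheduled samples.** Under SAP 4.1, when the nominal assessment is missing, "available assessments from the unscheduled visits within the protocol-defined target-study-day range may be mapped to the corresponding nominal visit". Table 10 (Appendix B) gives the windows and prefers the nominal visit.

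**Associations.** Protocol 7.12 says "Associations between immunogenicity data and PK as well as safety and efficacy data will be explored" and leaves the detail to the SAP. SAP Section 7 says "There are no changes to the analyses presented in the protocol".

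**The concern.** The reaction sample is drawn at the moment when ADA is most relevant to a participant's safety. The limb of the definition that will apply to anyone ADA negative at baseline does not mention it, and the other limb is open to it. Numerator and denominator then follow different rules: a post-dose result of any date can bring a participant into the set, but only certain dates can make that participant positive.

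Two things are at stake. ADA incidence could be understated by participants with transient or between-visit antibodies. Their status would also carry into the PK parameter summaries and concentration plots that SAP 6.2 and 6.3 split by treatment-emergent ADA. In addition, an exploration announced in the protocol would be carried out only for PK, without that being declared. SAP Section 1 says the SAP prevails where methods differ, so silence could be read as removal.

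**Working it through.** **1. When can an unscheduled sample reach an ADA visit?** Inputs are the Table 10 windows; length = last day − first day + 1.

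| ADA visit | Window | Days |
|---|---|---|
| Day 29 | 24–34 | 11 |
| Day 90 | 76–104 | 29 |
| Month 6 | 150–210 | 61 |
| Month 11 | 300–360 | 61 |

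Total: 11 + 29 + 61 + 61 = 162 days.

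- Days 1–23: none covered.
- Days 5–23, the early period in which Section 6.8.2 calls for the sample: 0 of 19.
- Days 5–29: Days 24–29 are covered, so 6 of 25 (24%).
- Day 5 to Day 420 (the Month 14 target): 162 of 416 (38.9%).
- Against the SAP's own onset categories for hypersensitivity (5.8.1.9): Days 5–8, 9–14 and 15–21 have no covered day; Days 22–29 have 6 of 8.

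These are calendar days, not participants or samples. They show when a sample can count, not how many will be lost.

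**2. Follow one participant through the rules.** Take a participant who is ADA negative at baseline, has a confirmed positive at a reaction visit, and has no positive scheduled sample. The days are illustrative.

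- Reaction sample on Day 12: outside every window. The participant is in the Immunogenicity Set, fails the baseline-negative limb, and is counted as not treatment-emergent.
- Reaction sample on Day 27, nominal Day 29 sample present: the nominal sample is used. Same result.
- Reaction sample on Day 27, nominal Day 29 sample missing: the reaction sample may be mapped to Day 29, and the participant then counts.

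Had the antibody persisted to a scheduled visit, the participant would have counted anyway. The gap concerns transient or between-visit ADA, or follow-up that ends before the next scheduled draw.

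**3. Does another SAP rule bring the sample in?** SAP 4.1 also uses unscheduled values for worst post-baseline results in safety analyses. Immunogenicity sits in 5.7 (Other Analyses), not in 5.8 (Safety Analysis), so that rule does not clearly reach it.

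**4. Protocol 7.12 against the SAP.**

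| Association with ADA | In the SAP? |
|---|---|
| PK | Yes: concentrations (6.2) and parameters (6.3) |
| Safety | No: none of the summaries in 5.8.1.9 is by ADA status |
| Efficacy | No: the subgroups in 5.6 include SARS-CoV-2 serostatus but not ADA |

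**5. Effect of one reclassification.** With 399 randomized 1:1, an arm has about 399 / 2 ≈ 200 participants, and the Immunogenicity Set can be no larger. Each reclassified participant moves that arm's ADA incidence by at least about 1 / 200 = 0.5 percentage points.

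**The case against.** The four visits named are exactly the scheduled post-dose ADA draws in SAP 3.4.3, so the parenthesis may only describe the schedule. Restricting incidence to scheduled visits is also defensible: every participant then has the same chances to test positive. The data are not hidden. SAP 4.1 lists all laboratory data by participant, SAP 6.2 names unscheduled PK samples, and SAP 6.3 uses every concentration regardless of window. Few participants can be involved: protocol Table 6-1 reports no hypersensitivity reactions through Day 4 in the first 200 participants, about half of the 399 randomized, and protocol 1.1.2.1 reports none in Phase 1. Finally, counting reaction-triggered draws and then tabulating reactions by ADA status gives participants with reactions more chances to be positive.

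Most of this stands as a limit on size and on the remedy. The descriptive reading is possible, but a programmer following the text would apply the list, and the other limb has none. Equal ascertainment is a good reason to keep a scheduled-visit table; the SAP does not offer it as a reason for the restriction. A listing does not correct the incidence endpoint. The unequal-sampling point is right, and any summary of reactions by ADA status has to deal with it.

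**Conclusion.** The point holds in a limited form. For baseline-negative participants, a positive found only on the reaction sample does not count toward treatment-emergent ADA, except by substitution for a missing nominal sample inside a window. Days 5–23 matter most, because Section 6.8.2 triggers the visit only after Day 4. The exploration of ADA against safety and efficacy announced in protocol 7.12 is absent from the SAP and not declared in its Section 7.

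The number affected is unknown and probably very small. No primary or key secondary result changes. The conclusion assumes that the visit list in 5.7.2 is applied literally.

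A reader might infer more than the documents support:

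- That the whole definition is restricted. Only the baseline-negative limb is.
- That the reaction samples are never used. The ADA results are listed and the PK results are analyzed.
- That the protocol promises an analysis of ADA by hypersensitivity. It says safety data in general; hypersensitivity is the natural candidate because it triggers the extra sample.
- That Days 1–4 are lost sampling days. Section 6.8.2 may not call for a sample then; its wording and that of 6.4.1.1 need to be reconciled.
- That injection site reactions should be tabulated by ADA too. No extra ADA sample is tied to them, and they are solicited on Days 1–4, well before the first scheduled post-dose ADA draw on Day 29.

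**What to change.** 1. In SAP 5.7.2, replace the visit list with *any valid post-dose sample, scheduled or unscheduled*, and apply it to both limbs. Keep the scheduled-visit table as the equally ascertained incidence.
2. Add a listing that pairs each hypersensitivity reaction with its ADA and PK results.
3. Add a descriptive summary of hypersensitivity by treatment-emergent ADA status and arm, shown both with and without the reaction-triggered samples, so that the effect of the extra sampling is visible.
4. Either add efficacy by ADA status or declare its omission in SAP Section 7.

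The cost is a phrase in the SAP, one listing and one small summary from data already collected, plus either an efficacy summary or a sentence in Section 7. Reported ADA incidence may rise slightly.
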